14.2.1 SAE and Unresolved AE Follow-Up

Follow-up information for SAEs and information on non-serious AEs that become serious should also be reported to the Medical Monitor as soon as possible using the SAE Report Form.

The patient should be followed until it is determined that the event resolved, stabilized, or in the opinion of the Investigator the event is not going to improve due to underlying disease, or the patient is lost to follow-up.

Investigators must report SAEs and follow-up information to their responsible HREC according to the policies of the responsible HREC.

The detailed SAE reporting process will be provided to the sites in the SAE reporting guidelines contained in the study reference manual.

14.2.2 Investigator Reporting of AEs/SAEs/Deaths after Study Discontinuation

Thirty days after completing protocol-specific treatment or study discontinuation, treatment related AEs, SAEs, or deaths determined by the Investigator as treatment related are to be reported directly to the Sponsor.

At the last scheduled study visit, the Investigator should instruct the patient to report to the Investigator any subsequent SAEs that the patient or the patient's personal physician believes could be related to prior study treatment.

SAEs after study discontinuation considered related to study treatment are to be sent to the Sponsor.

14.2.3 Sponsor SAE Reporting Requirements

The Sponsor is responsible for reporting relevant SAEs/Suspected Unexpected Serious Adverse Reactions (**SUSARs**) to the competent authority, regulatory authorities (e.g. TGA), and participating investigators, in accordance with International Council on Harmonization (ICH) guidelines and/or local regulatory requirements.

The Sponsor is responsible for reporting **unexpected fatal or life-threatening events** associated with the use of the trial drugs to the regulatory agencies and competent authorities via telephone or fax **within 7 calendar days** after being first notified of the event. The Sponsor will report all related but unexpected SAEs including **non-death/non-life-threatening related but unexpected SAEs** associated with the use of the trial medications to the appropriate competent authorities (according to local guidelines), investigators, and relevant HREC by a written safety report **within 15 calendar days of notification**.

15 CONDUCT OF STUDY

15.1 HUMAN RESEARCH

The Protocol and all other relevant study documents (informed consent, advertising etc) will be submitted to the site Human Ethics Review Committee (HREC) and to regulatory authorities in the countries where the study will be conducted.

Written confirmation of approval (noting version/ date of all approved documents) must be received by the Investigator before the study commences and approval of all documents pertaining to this study will be kept in the study Master file.

The HREC will have at all times the right to review all source documentation.

15.2 GOOD CLINICAL PRACTICE

The study will be conducted in accordance with the principles of good clinical practice (GCP) using the guidelines established in 1996 by the International Council on Harmonisation (ICH), annotated in July 2000 by the TGA.

Compliance with these guidelines ensures compliance with the currently approved version of the Declaration of Helsinki (October 2000) with notes of Clarification in 2002 (Washington) and 2004 (Tokyo) and any local legal and regulatory requirements.

15.3 ADHERENCE TO PROTOCOL

No changes or deviations in the conduct of this protocol will be permitted, with the exception of emergency situations. The Investigator should contact the Sponsor by telephone as soon as possible. The nature and reasons for the protocol deviation should be recorded in the CRF.

In the event of an emergency, the Principal Investigators will institute any medical procedures deemed appropriate. However, all such procedures must be promptly reported to the Sponsor, the Medical Monitor, and the HREC.

Protocol violations are defined as any deviation from this protocol, and include items such as a study required evaluation not completed according to the protocol, a study visit completed outside of the defined visit window, etc.

A major protocol violation would include, but not be limited to, the following:

- enrolment of a patient who does not meet the inclusion/exclusion criteria.
- enrolment of a patient who has not provided informed consent
- the non-reporting of serious adverse events according to protocol and regulatory requirements

All protocol violations will be reported to the Sponsor via a protocol violation form. Major protocol violations must be reported to the Sponsor as soon as the Investigator or the Data Monitor becomes aware of them.

All major protocol violations will be reported to the Human Research Ethics Committee (HREC) with response and approval required for any change or deviation that may increase risk to the Patient, and/or that may adversely affect the rights of the Patient or validity of the investigation.

15.4 PROTOCOL AMENDMENTS

Amendments to the protocol need to be approved by the Sponsor and the Study Steering Committee. Major amendments will require the approval of the HREC. Minor amendments will require that the HREC be notified. Any amendments affecting the involvement of patients would require all patients being notified.

16 PATIENT INFORMED CONSENT

The patient informed consent form contains the 20 elements required for the provision of informed consent as described in ICH E6(R2) 4.8. in accordance with the Code of Federal Regulations (21 CFR 50.25) and the latest amendment of the Declaration of Helsinki (October 2013). Additionally, the informed consent form has been reviewed and approved by the Sponsor and the study HREC prior to initiation of the study.

The Principal Investigator, or a person designated by the investigator, is responsible to explain the nature of the study and the risks and benefits of taking part to the patient in order to obtain the patient's written consent. It should be stressed that participation is voluntary. The patient can refuse to participate and is free to withdraw from the study at any time, without affecting their future medical management.

Prior to undertaking any study specific activity, the Investigator should explain the nature of the study to the patient, including providing a written information sheet which should be read and retained by the patient. All patients must give fully informed consent, which must be obtained in writing by a personally dated signature and witnessed. The signed consent form should be available to be viewed by the Clinical Study Monitor and a copy of all consent documents provided to the patient.

Patients must be informed that representatives of the Sponsor, HREC and regulatory authorities may inspect their medical records in order to verify the accuracy and authenticity of study documentation including information entered in the eCRF. Patients must be informed as to the nature of the privacy guidelines in place to protect their anonymity.

Any amendments to the Informed Consent Form will need to be approved by the Sponsor and the HREC.

17 DISCLOSURE OF DATA

17.1 CONFIDENTIAL INFORMATION

Patient medical information obtained during the study is confidential and disclosure to third parties other than those noted below is prohibited. All patients will be assigned a study identification number.

Patients will be identified on case report forms only by their patient number and initials.

At the patient's request, medical information may be given to his or her personal physician or other appropriate medical personnel responsible for his or her welfare.

Data generated by this study must be available for inspection on request by representatives of state and federal health authorities, the Sponsor, and the HREC.

All published information from this study will be presented in such a way that it does not permit identification of individual patients. Patient identity will remain protected except as required by regulatory or legal inquiries.

To fully evaluate patient safety issues that may arise during the study, Sponsor, or state and federal authorities will require direct access to source documents including trial-related monitoring, audits, HREC review and regulatory inspection(s).

It must be explained to the patient before enrolment into the study that the patient's Protected Health Information (PHI) obtained during the study may be shared with the study, Sponsor, state and federal authorities, and HREC regulatory inspections(s).

17.1.1 Study records and source documents

All clinical information obtained by the Investigator is confidential, including that supplied by the Sponsor, and disclosure to third parties must be limited to:

- i. Those undertaking legitimate peer review of the scientific and ethical aspects of the study such as, but not limited to, the TGA and/or FDA.
- ii. Other staff participating in the study, so that necessary medical care can be undertaken.
- iii. The patients, so that written informed consent can be obtained.
- iv. Representatives of the sponsor, including the Monitor(s).

Patients will be identified to the sponsor and regulatory authorities only by their study number and initials recorded on the CRF. Other patient details are to be obscured if a document is being forwarded to the Sponsor with the CRF or provided to regulatory authorities for review.

The Investigator will maintain a patient screening and enrolment log (patient numbers and the corresponding patient names) to enable the records to be identified.

17.1.2 Prior to study commencement

Prior to the release of clinical study supplies and the study commences, the following documents will be collected from the Principal Investigator:

- i. An up-to-date, signed and dated Curriculum Vitae for all Investigators and other study staff.
- ii. The signed Protocol and any amendments.
- iii. The signed clinical study agreement (CSA).
- iv. The signed letter from the HREC giving approval for the study (version numbers/dates of all approved documents to be included), together with a letter of constitution of the HREC. Copies of any other correspondence with the HREC relevant to the study should also be supplied.
- v. The signed letter from the relevant national authority acknowledging the study.
- vi. Current laboratory certification of the laboratory(ies) performing analysis, as well as current normal laboratory ranges for all laboratory tests.

The Investigator shall provide to the Sponsor all observations and test results required in the protocol and indicated in the CRFs. In particular, all details of adverse events, as defined in the protocol should be supplied.

17.1.3 Document retention

The Principal Investigator will retain copies of the following documents in a secure place for a period of 15 years from completion of the study per Therapeutic Goods Administration (TGA). These documents may be retained for a longer period by agreement with the Sponsor.

- i. A signed copy of the Protocol and any amendments.
- ii. Copies of the patients' Case Report Forms and Data Clarification Forms.
- iii. The patient informed consent documents.
- iv. Copies of the Curricula Vitae of the Investigator and study staff.
- v. Copies of all correspondence with the HREC and national regulatory authority.
- vi. Copies of relevant laboratory ranges.
- vii. Copies of all correspondence to and from the Sponsor and the Monitor and the Investigator.
- viii. The patient's original clinical notes.

The Sponsor will provide the Principal Investigator with information concerning the current status of the investigational drug as it relates to the Investigator's obligation for the retention of study records.

The Investigators should contact the Sponsor prior to disposing of any such records. The Sponsor will arrange for continued storage of all records, if necessary and as documented in the Clinical Study Agreement.

The Sponsor will maintain correspondence with the Principal investigator after study closeout to ensure that study documentation is retained for the appropriate amount of time. The investigator must inform the Sponsor immediately if any documents are to be destroyed, to be transferred to a different facility, or to be transferred to a different owner.

In the event the investigator withdraws from the study (e.g., relocation, retirement), the records shall be transferred to a mutually agreed-upon designee (e.g., another investigator). Notice of such transfer will be given in writing to the Sponsor.

17.1.4 Access to source documents

To ensure the accuracy of the data collected in the CRFs, representatives from the Sponsor, Regulatory Authorities and the Monitor may require access to source documents (i.e. patient records, patient charts, laboratory reports, X-ray reports and scans). Anonymity of the patient will be maintained at all times.

17.1.5 Publication policy

To avoid disclosures that could jeopardize proprietary rights, Investigators are required to submit all publications to the Sponsor prior to submission to a publisher. The Sponsor will review any such submissions within 30 days of receipt. Permission to publish will not be withheld unreasonably.

Details of the study will be registered prior to commencement at www.clinicaltrials.gov, with information updated throughout the course of the trial. Publication in medical or scientific journals will conform to guidelines set out in the International Committee of Medical Journal Editors (ICMJE)¹, and consult reporting standards such as the CONSORT² group and the individual journals.

Available on <http://www.icmje.org> and on <http://www.consort-statement.org>

18 ADDITIONAL PATIENT CARE DURING POST-STUDY

18.1 EMERGENCY CONTACT

18.1.1 Investigator

The Principal Investigator, or nominated deputy, will be available for consultation by the patient at any time during the study period. Names and telephone numbers of staff responsible for the study will be made available to the patient. The Investigator must ensure that adequate medical care is provided for any adverse events. The Investigator should inform the patient when medical care is required for any intercurrent illness.

18.1.2 Sponsor

In an emergency, the Principal Investigator should contact both the study Sponsor and the Monitor by telephone.

18.1.3 Liability and Insurance

With effect from the commencement of the study, the Sponsor will indemnify study participants according to the local institutional regulations concerning clinical study involvement.

20 APPENICES

20.1 APPENDIX 1- ECOG SCORE*

Grade	ECOG
0	Fully active, able to carry on all pre-disease performance without restriction
1	Restricted in physically strenuous activity but ambulatory and able to carry out work of a light or sedentary nature, e.g. light house work, office work
2	Ambulatory and capable of all self-care but unable to carry out any work activities. Up and about more than 50% of waking hours.
3	Capable of only limited self-care, confined to bed or chair more than 50% of waking hours
4	Completely disabled. Cannot carry on any self-care. Totally confined to bed or chair.
5	Dead

* As published in Am. J. Clin. Oncol.: Oken, M.M., Creech, R.H., Tormey, D.C., Horton, J., Davis, T.E., McFadden, E.T., Carbone, P.P.: Toxicity and Response Criteria Of The Eastern Cooperative Oncology Group. Am. J. Clin. Oncol. 5:649-655, 1982. Eastern Cooperative Oncology Group, [name]., Group Chair.

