10.2.1 Screening Visit (VS)

The purpose and the procedures of the Study will be fully explained to participants at the screening visit and every patient approached regarding the study will be provided with the Informed Consent Form (ICF). Patients wishing to enrol in the Study will sign the ICF prior to initiating any study related investigations or procedures.

All screened patients who sign the ICF must be recorded on the Screening/Enrolment Log. If a patient who signs an ICF is not enrolled in the study, the reason will be noted. The Screening/Enrolment Log will be retained within the Investigator Site File.

The following procedures are to be performed at the screening visit to occur within 2 weeks of commencement of NOX66 treatment:

- Obtain Informed Consent
- Review and confirm eligibility (Inclusion / Exclusion Criteria)
- Medical History and Demography, including review of any prior radiation therapy and toxicities / adverse events
- Physical Examination including vital signs
- Performance Status Assessment (using ECOG performance scale)
- Safety blood sampling – Complete Blood Count, Serum Chemistry, and Urinalysis; and results within 5 days of enrolment
- Blood sample for serum PSA and testosterone
- Electrocardiography (12-lead) in triplicate
- Concomitant Medication Review
- Tumour Imaging (CT/MRI) including measures of target lesions- baseline
- Administration of Brief Pain Inventory -Short Form questionnaire

Radiological scans performed prior to consent may be utilized for the purposes of the study if they have been performed as part of routine clinical practice and the patient consents for their medical records to be reviewed by the Sponsor, the scans were performed in the 28 days prior to the screening visit (i.e. they can be considered current evidence of tumour size) and they can provide suitable tumour measurements and assessments of target and non-target lesions.

The Principal Investigator will maintain a confidential log of all patients who have been screened for participation in the study whether or not the patient was eligible for study participation

10.2.2 Enrolment Visit (V1):

Once eligibility is confirmed patients will be contacted to attend clinic for:

- education on self-administration and dispensing of NOX66 for use from Day 1 of the treatment cycle
- baseline biomarker blood sample for idronoxil

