Patient may be contacted by telephone after enrolment as a reminder to start NOX66 administration day prior to attending clinic for radiation therapy.

10.2.3 Treatment Cycle (Days 1-16) - Visits 2 to 7

Treatment will Commence on Day 1 of the Study Visit Schedule (Table 1) and the procedures for Treatment Visits are listed below in Table 1.

Overall, the patient will attend the clinic on 7 days during the Treatment Cycle.

During the Treatment Cycle, the patient will receive treatment of:

- NOX66 (Dose dependent on treatment cohort) for 13 up to 16 consecutive days (Days 1-16), inclusive of weekends and public holidays.
- Palliative radiation therapy (20Gy Dose) in five fractions over 8 days commencing on Day 2 to Day 9. Radiation therapy **not given** on weekends and public holidays.

Table 1. Schedule of Assessments: TREATMENT CYCLE

Period	Pre-RT		RT									Post RT					EoT ³
	D0 (-7)	D 1	D 2	D 3	D 4	D 5	D 6	D 7	D 8	D 9	D 10	D 11	D 12	D 13	D 14	D 15	D 16+1
VISITS	V1 ¹		V2	V3 - V6 ²													V7
NOX66 (Self-administration)		X	X	X	X	X	X	X	X	X	X	X	X	X	X	X	X ⁴
Radiation therapy			X	X													
Physical exam			X														X
ECG																	X
Vital Signs			X														X
Complete Blood Count																	X
Serum chemistry																	X
Urinalysis																	X
Biomarker ⁵	X																X
BPI-SF ⁶ Questionnaire																	X
Concomitant medications/ Adverse Event ⁷ review			X	X													X
Dispense NOX66	X																
Return NOX66																	X

¹Enrolment-Visit to occur after eligibility confirmation (Screening) and prior to V2, to receive NOX66 and education on self-administration

² Patient attend clinic for 5 days in an 8-day period to receive RT. Patient will not attend clinic on days where RT is not conducted

³ End of Treatment (EoT) visit to occur Day following last dose of NOX66

⁴NOX66 dosing continues to Day 16 if there has been (weekend and public holiday -up to 3 days) interruption in RT in Treatment Cycle.

⁵ Biomarkers include idronoxil

⁶ Brief Pain Inventory-Short Form (1991)

⁷ Adverse Event (AE) assessed by Investigator using the NCI CTCAE v4.03 scoring system

10.2.4 Six-Week Follow up (Day 43 ± 5) - Visit 8

Visit 8 will occur 28 days/4 weeks post completion of NOX66 treatment and consist of the following assessments:

- Physical Examination including vital signs
- Performance Status Assessment (using ECOG performance scale)

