Safety Analysis: The safety will be assessed through the analysis of the reported incidence of treatment emergent AEs, including SAEs, dose-limiting toxicities, AEs leading to withdrawal, events of at least CTCAE Version 4.03 Grade 3 in severity, and AEs related to study treatment. Treatment emergent AEs are those with an onset on or after the initiation of therapy. Other safety endpoints include laboratory results, physical examinations, vital signs, and changes in ECOG status. A copy of CTCAE Version 4.03 scoring system may be downloaded from:

http://evs.nci.nih.gov/ftp1/CTCAE/CTCAE_4.03_2010-06-14_QuickReference_8.5x11.pdf.

The adverse events will be summarized by MedDRA coding terms, System Organ Class (SOC), and preferred term for all treated patients and by dose cohort. The AEs will also be tabulated by maximum severity and maximum relationship to study drug where applicable. The number and percent of patients experiencing dose-limiting toxicities will be summarized by dose cohort, by DLT, and system organ class for all treated patients. Other safety endpoints, which include change from baseline in laboratory results and vital signs, and shifts in physical examinations, will be summarized throughout the study by visit for each dose level for all treated patients.

Concomitant medications: are to be listed for all patients.

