13.2 SAFETY DATA MONITORING

The Study Steering Committee (SSC) will review and evaluate all toxicities causally associated with NOX66 treatment and or the radiation therapy combination therapy. The SSC will consist of:

- Principal Investigator from each clinical site, or medical designee
- Sponsor's Medical Monitor
- CRO Medical Representative (if applicable)
- Director of Clinical Development, Noxopharm Ltd

Review of any adverse events of Grade 2 toxicity and above, considered by the Principal Investigator to be related to idronoxil (NOX66), will be reported to the SSC immediately and decision on the continuation of the patient individually, and the study in general, will be provided.

The Study Steering Committee will review the Safety Data and determine dose cohort escalation following completion of treatment cycle (Visit 7) of final patient in a cohort.

The SSC will determine the dose for cohort expansion based on the review of accumulated safety data, on treatment response and disease evaluation following WEEK 6 assessments of all patients and determine continuation of the study.

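### ECOG change is a named safety endpoint but, unlike the three endpoints listed with it, is not measured at end-of-treatment Visit 7 or at any visit from Visit 1 to Visit 7

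*Combined protocol and SAP*

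**What the plan says.** Section 12.2, Safety Analysis, states: "Other safety endpoints include laboratory results, physical examinations, vital signs, and changes in ECOG status". No timepoint is attached to any of the four. The ECOG scale itself is in Appendix 1 (section 20.1), where grade 3, for example, is defined as "Capable of only limited self-care, confined to bed or chair more than 50% of waking hours".

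ECOG is first recorded at the screening visit (section 10.2.1), within two weeks before NOX66 starts, as "Performance Status Assessment (using ECOG performance scale". The treatment cycle is governed by "Table 1. Schedule of Assessments: TREATMENT CYCLE" in section 10.2.3. It has rows for physical examination, vital signs, blood count, chemistry, urinalysis, ECG, BPI-SF and adverse event review, but none for ECOG. The enrolment visit (section 10.2.2) has no ECOG either. On the timing of Visit 7, a footnote to Table 1 says: "End of Treatment (EoT) visit to occur Day following last dose of NOX66".

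The next ECOG is at the "Six-Week Follow up (Day 43 ± 5) - Visit 8" (section 10.2.4), with the note that "Visit 8 will occur 28 days/4 weeks post completion of NOX66 treatment". Later grades follow at Week 12, Week 24, Month 9 and Month 12.

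Section 13.2 has the SSC review the safety data and "determine dose cohort escalation following completion of treatment cycle (Visit 7) of final patient in a cohort".

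**The concern.** The primary objective (section 6.1) is the safety and tolerance of a short course of NOX66 given with palliative radiation. An endpoint named for that purpose should have a value that relates to the course. Three of the four endpoints in the section 12.2 sentence have one at Visit 7. ECOG does not, and the protocol gives no reason for treating it differently, so this looks like an omission from Table 1.

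Two things are at stake. The safety summary cannot show performance status at the end of treatment at any dose level. And when the SSC reviews a cohort after its last Visit 7, the one clinician-graded measure of overall function in the plan is missing for at least that last patient.

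**Working it through.** The protocol gives no figure to reproduce here. The check compares the visit lists and does day arithmetic.

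**1. The four endpoints against the schedule** (Table 1 and section 10.2.4)

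| Endpoint in 12.2 | Visit 2 | Visits 3-6 | Visit 7 | Visit 8 |
|---|---|---|---|---|
| Laboratory results | no | no | yes | yes |
| Physical examination | yes | no | yes | yes |
| Vital signs | yes | no | yes | yes |
| ECOG | no | no | **no** | yes |

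ECOG is listed only at screening (10.2.1) and at Visits 8, 9, 10, 11 and 12 (10.2.4, 10.2.5, 10.2.7, 10.2.8, 10.2.9). Scheduled readings from Visit 1 to Visit 7: 0.

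**2. Timing**

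- Last NOX66 dose: Day 13 to Day 16 (section 10.2.3).
- Visit 7 = last dose + 1: 13 + 1 = Day 14, to 16 + 1 = Day 17.
- Visit 8 window: 43 − 5 = Day 38, to 43 + 5 = Day 48.
- Visit 7 to first post-baseline ECOG: shortest 38 − 17 = 21 days, longest 48 − 14 = 34 days. At the nominal Day 43 it is 43 − 17 = 26 to 43 − 14 = 29 days.
- Last dose to first post-baseline ECOG: 38 − 16 = 22 to 48 − 13 = 35 days. The four weeks stated in 10.2.4 are therefore nominal and not guaranteed.
- Screening to first post-baseline ECOG: up to 14 + (48 − 1) = 61 days. This is not a hard limit, since section 8.4 allows for start delays beyond two weeks.

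Section 10.4.7 gives Visit 7 as Day 16 ± 1. That yields 38 − 17 = 21 to 48 − 15 = 33 days, inside the same range.

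**3. Which decisions lack the grade**

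- Dose for Cohorts 2 and 3 (sections 10.2.14 and 13.2): triggered by Visit 7 of the cohort's last patient. These two decisions draw on Cohorts 1 and 2, 4 + 4 = 8 patients.
- The last patient has no post-baseline ECOG at that trigger. Another patient in the cohort has one only if he started at least 38 − 17 = 21 to 48 − 14 = 34 days before the last, depending on course length and visit window. Accrual speed is not stated, so the number with a grade is unknown.
- Expansion dose (sections 10.2.14 and 13.2): decided after Week 6 assessments, when ECOG has been collected.

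**4. Whether the stated rule would change.** Section 10.2.14 escalates, holds, reduces or pauses according to the number of discontinuations for NOX66-related adverse events. ECOG is not an input, so a Visit 7 grade would leave the rule's result unchanged. It would enter only the wider safety review in section 13.2.

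**5. How it would be reported.** The section 12.2 sentence promising summaries by visit and dose level names laboratory results, vital signs and physical examinations. It does not name ECOG, so the tabulation also needs to be specified.

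**The case against.** A reader might infer that functional decline during treatment goes unseen and that the SSC raises the dose without knowing of it. The documents do not support that.

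- CTCAE adverse events are reviewed at Visit 2, Visits 3 to 6 and Visit 7. Significant changes on follow-up physical examination are to be reported as adverse events (10.4.2). Events of Grade 2 and above judged related to NOX66 go to the SSC at once (13.2).
- Fatigue above Grade 2, the example in section 5.3, is a toxicity grade and is captured directly by that review.
- The BPI-SF at Visit 7 asks about interference with activity, walking and work.
- The primary outcome measures (10.1) are toxicity events, related adverse events and DLT or MTD. ECOG is a secondary measure there, is counted under efficacy in the synopsis and in 12.2, and can be analysed from Week 6 onward. On this view, how often to measure it is a matter of preference.

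Most of this stands, and it limits the point. It does not remove it. The BPI-SF items concern interference from pain only, so they do not grade decline from other causes. Section 14 excludes expected worsening of pre-existing conditions from adverse events, so decline attributed to advanced cancer could go unreported, whereas an ECOG grade needs no attribution. And section 12.2 does name ECOG change as a safety endpoint, whatever its other roles.

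**Conclusion.** The point holds in a limited form, as a cheap improvement. Section 12.2 and Table 1 do not match: a named safety endpoint has no scheduled value during or at the end of the course for any of the up to 24 patients, and its first value comes 21 to 34 days after Visit 7. The loss falls on the end-of-treatment safety summary and on the SSC's general safety review for the two decisions triggered at Visit 7. It does not fall on the numeric escalation rule or on the expansion decision.

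It would go too far to say that a patient who declined on treatment will have recovered by Week 6 and be recorded as unchanged. The interval makes that possible on the ECOG endpoint alone, but nothing in the documents shows that it happens, and the cause could still be recorded as a graded adverse event. The day ranges assume courses of 13 to 16 days and visits kept within their windows.

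**What to change.** Add an ECOG row to Table 1 with a reading at Visit 7. In section 12.2, specify a table of the shift in ECOG grade from baseline to Visit 7 by dose level, and keep the Week 6 and later grades for later change. In section 13.2, include the Visit 7 grades in the safety data the SSC reviews. Leave the dosing and escalation rules as they are. A reading at Visit 2 is not needed: it falls on Day 2, after one day of NOX66, and would do little more than refresh the baseline.

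The cost is one CRF field at a visit where the patient is already examined, and a minor amendment. No new visit, staff or procedure is required. An end-of-treatment grade that was not recorded cannot be supplied by later visits. If the sponsor chooses not to collect it, section 12.2 should at least say that ECOG change is assessed from Week 6 onward only.
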